13. CLINICAL INVESTIGATION PROCEDURES

Up to 30 subjects with documented clinical symptoms, ECG changes and study lesion identified by angiography requiring Coronary Atherectomy will be enrolled in this study.

A written informed consent form will be obtained for enrollment. Each patient will be assigned a unique identification number. Only patients eligible to undergo cardiac catheterizations as per routine practice will be considered for the study. Premedication of patients will be as per the investigator's routine practice. All data will be captured in Case Record Form.

13.1 SCREEN FAILURE:

There may be a provisionally enrolled subject who withdraws consent prior to the index procedure or is unsuitable for the Excimer Laser Coronary Atherectomy (ELCA[®]) following laboratory assessments, pre-procedure ECG or any study specific invasive or non-invasive treatment as pre-specified in the Clinical Investigation Plan. These subjects will be exited from the study once screen failure is confirmed. Subject informed consent forms will be kept in the site's administrative files. These subjects will not be considered as part of the 30 patients for the analysis.

13.2 ENROLLED:

The investigator must ensure that all patients being considered for the study meet the study criteria (all of the inclusion and none of the exclusion criteria). The investigator should apply no additional exclusions, in order that the study population will be representative of all eligible patients. Patient selection is to be established by checking through all inclusion/ exclusion criteria at screening and baseline. A relevant record (e.g. checklist) must be stored with the source documentation at the study site. Deviation/Violation from any entry criterion excludes patients from enrollment into the study.

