13.3 INCLUSION CRITERIA

Subjects will be enrolled in the study if ALL of the following conditions are met:

1. Patient 18 years to 75 years, both inclusive
2. Have at least one severely stenotic lesion (greater than or equal to 80% diameter stenosis as assessed by visual estimation)
3. Haemodynamically stable patients coming to the site for cardiac catheterization and angiography for various indications and who fulfill all the following criteria:

Spectranetics Corporation

Study Protocol Number: ELCA-1016

Version 1.0

Dated: 12 Oct 2016

- Have no clinically significant cardiac arrhythmias, based on ECG results
 - Have no evidence of valvular pathology, based on echocardiogram results
 - Have $\geq 30\%$ left ventricular ejection fraction (LVEF), based on echocardiogram results.
4. Angiographic evidence of calcification or a chronic total occlusion
 5. Vessel reference diameter greater than or equal to 2.0 mm
 6. Patient is willing and able to comply with study requirements
 7. Women of child bearing potential , willing to use at least two methods of contraception

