13.5 SCHEDULE AND PROCEDURES

Prescreening Evaluation, Informed Consent & Enrollment

The subjects being considered for percutaneous coronary interventions should be pre-screened via a general review of inclusion/exclusion criteria without any study related assessment.

After the subject signed the IRB/IEC approved informed consent, study specific screening assessments can be started and the subject is provisionally enrolled.

Each potential subject who meets the inclusion criteria and has none of the exclusion criteria will be explained about the study and study device, informed about the objective, potential risks-benefits and alternatives of the study and then invited to voluntarily participate in the study. Subjects will be informed about the one month (30±7 days) follow up visit to assess the safety and efficacy endpoints. Investigator will answer each questions asked by subject and/or subject's representative during the informed consent process.

Investigator will give ample time to subject and/or subject's representative to read and understand the informed consent form. If a subject and/or subject's representative voluntarily agrees to participate in the study, subject and/or subject's representative will sign and date the written subject informed consent form prior to any study procedure. Each subject is free to withdraw from the study at any time during the study period.

Informed consent should be obtained in accordance with the applicable Indian regulations - Schedule Y and all applicable amendments (Drugs and Cosmetics Rules, 1945), GCP for Clinical Research in India (2001), ICMR guidelines for Biomedical Research on Human Subjects (2006), and current versions of Declaration of Helsinki, ICH-GCP and ISO 14155. If a subject might be eligible for the study, the investigator or delegated staff should approach the subject to obtain the written informed consent. During the consent process the background of the proposed study, the benefits and risks of study participation should be explained in detail to the subject.

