13.6 SCREENING/BASELINE EXAMINATIONS

After signature of the informed consent, the subjects will undergo a baseline examination in order to assess their eligibility through the following tests and examinations

- Physical examination and relevant medical history, including angina status or myocardial ischemia assessment as per Canadian Cardiovascular Society (CCS) Classification, medication list, vital signs and subjects demographic information;
- Baseline cardiac biomarkers (CK, CK-MB and Trop I) must be obtained 24 hours prior to the index procedure;
- Routine clinical laboratory testing including Complete Blood Count (CBC) and platelet count and blood chemistry include serum sodium, potassium, urea, creatinine, and random blood sugar (RBS) must be obtained, 72 hours prior to the index procedure;
- For women of child bearing potential, urine pregnancy test must be performed 72 hours prior to the index procedure and it must be negative;
- 12-lead electrocardiogram must be obtained 24 hours prior to the index procedure.
- Documented LVEF through the Echocardiography or LV angiography to assess Left Ventricular function 72 hours prior to the index procedure.
- Review of inclusion and exclusion criteria

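### Three device contraindications in section 10.3 (unprotected left main, bifurcation, not a bypass candidate) are missing from the eligibility lists, while section 13.2 tells investigators to add no exclusions

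*Protocol*

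**What the plan says.** Protocol section 10.3 lists five contraindications to ELCA. Three concern where the lesion lies or who the patient is: an unprotected left main lesion, a lesion within a bifurcation, and a patient who could not be accepted for bypass surgery. The other two concern access: the catheter cannot reach the lesion, or the guidewire cannot cross it.

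Eligibility is set elsewhere. Section 13.3 opens with "Subjects will be enrolled in the study if ALL of the following conditions are met" and gives seven inclusion criteria; 13.4 gives fifteen exclusions. Section 13.2 asks that patients "meet the study criteria (all of the inclusion and none of the exclusion criteria"), states that "Patient selection is to be established by checking through all inclusion/ exclusion criteria at screening and baseline", and adds: "The investigator should apply no additional exclusions, in order that the study population will be representative of all eligible patients".

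The earlier and later checks use the same lists. Before consent, patients are "pre-screened via a general review of inclusion/exclusion criteria without any study related assessment" (13.5). The baseline work-up in 13.6 ends with "Review of inclusion and exclusion criteria". Neither mentions 10.3.

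**The concern.** The protocol states when the device must not be used, but does not make those conditions grounds for keeping a patient out. It also tells investigators not to go beyond the listed grounds. A site that follows 13.2 literally can enrol a patient whose only target lesion may not be lasered.

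The stakes are patient safety and clear instructions to sites. Bypass candidacy matters because section 11 lists emergency cardiac surgery among the risks of the device, and section 9 records that the original approval was for patients who were acceptable bypass candidates. For bifurcation lesions the background could even mislead. Section 9 names them among the lesions in which balloon angioplasty does less well, and says that some of these may be better handled by excimer laser.

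**Working it through.** No figure in the plan needs reproducing. The check compares sections.

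**Step 1. Are the contraindications in the lists?** Each item of 10.3 was compared with all 7 + 15 = 22 criteria.

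| Contraindication (10.3) | Matching criterion in 13.3 or 13.4 |
|---|---|
| Unprotected left main | None |
| Within a bifurcation | None |
| Not a bypass candidate | None; exclusion 12 overlaps in part |
| Catheter cannot reach | None |
| Guidewire cannot cross | None |

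Result: 0 of 5 carried over. The synopsis lists have the same 7 + 15 items and also carry 0 of 5.

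**Step 2. Does any criterion restrict lesion location?** Three of the 7 inclusions describe the lesion or vessel: number 2 (stenosis of at least 80%), number 4 (calcification or chronic total occlusion) and number 5 (reference diameter of at least 2.0 mm). None of the 15 exclusions does. None of the 22 concerns location. A patient whose only severe lesion is a calcified 80% stenosis of an unprotected left main, or within a bifurcation, in a vessel of at least 2.0 mm can therefore meet every criterion.

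**Step 3. Does any eligibility check bring 10.3 in?** There are three: pre-screening (13.5), the baseline review (13.6) and the checklist (13.2). Each names only the inclusion and exclusion criteria, so 0 of 3 refer to 10.3.

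**Step 4. Which contraindications need an entry rule?** Section 10.2 describes use after a guidewire has been placed across the target site. The wire and reach items therefore largely limit themselves, which leaves 5 − 2 = 3: left main, bifurcation and bypass candidacy.

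**Step 5. Why not simply add all five?** Device Success (12.5) is the laser catheter crossing the whole lesion. Whether the catheter reaches or the wire passes is often known only during the procedure. If these were entry exclusions, a failed attempt could later be called ineligible. As an illustration, assume one target lesion per patient, 30 patients and one failed crossing. Kept in, the rate is 29/30 = 96.7%. Removed, it is 29/29 = 100%. One failure is worth 1/30 = 3.3 percentage points, or 1/25 = 4.0 points with 25 patients.

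**The case against.** The strongest reply is that the protocol already stops these patients before treatment.

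- **Screen failure.** Section 13.1 lets a provisionally enrolled subject who is unsuitable for ELCA exit "following laboratory assessments, pre-procedure ECG or any study specific invasive or non-invasive treatment as pre-specified in the Clinical Investigation Plan", and leaves such subjects out of the 30. The schedule in section 8 places a coronary angiogram at screening. This route is real, so the investigator does not face a strict choice between breaching 13.2 and enrolling. But it takes a broad reading: the sentence speaks of treatment, does not name the contraindications, and stands next to the instruction to add no exclusions.
- **Rules on use.** Sections 10.7 and 13.8 require use according to the protocol and the IFU, and contraindicated use would fall under the violations in 16.7. This stands, and should prevent most such treatment. It governs use, however, not entry.
- **Purpose of 13.2.** Its aim is a representative population, so it may be directed only at investigators' own preferences. That is plausible, but its definition of the study criteria still omits 10.3.
- **Need for atherectomy.** The opening of section 13 asks for a "study lesion identified by angiography requiring Coronary Atherectomy". One can argue that a contraindicated lesion is not such a lesion. The words express need and do not rule out a contraindication.
- **Exclusion 12.** It covers patients unfit for bypass through co-morbid illness, at the investigator's discretion, but not for other reasons.

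A reader might also infer that being found unsuitable after consent is itself a fault. It is not: 13.5 makes enrolment provisional at consent, with study-specific screening to follow.

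**Conclusion.** The gap is real and limited. Three contraindications that do not limit themselves are absent from all 22 criteria and from all three eligibility checks, and 13.2 discourages sites from supplying them. Whether such a patient is stopped depends on how 13.1 is read, or on the operator applying 10.3 or the IFU.

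Two stronger readings are not supported. One is that the protocol permits lasering a contraindicated lesion: 10.7 and 13.8 bar it. The other is that the analysis population is necessarily distorted: a patient exited under 13.1 is not among the 30.

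The conclusion assumes that the patient has no other suitable target lesion; a multivessel patient with one is properly enrolled. It also assumes that the IFU, which is not at hand, carries the same contraindications as 10.3. The documents do not say how common such patients are, so the number affected cannot be estimated.

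**What to change.** 1. Add three exclusions to 13.4 and the synopsis: (a) the only target lesion is in an unprotected left main; (b) the only target lesion is within a bifurcation; (c) the patient could not be accepted for bypass surgery. This takes the exclusions from 15 to 15 + 3 = 18. Items (a) and (b) can be read from the screening angiogram.
2. Reword 13.2 so that investigators apply no exclusions beyond 13.3, 13.4 and the 10.3 contraindications evident before the procedure.
3. Do not make catheter reach or guidewire passage entry exclusions judged after an attempt. State that once the procedure has started, a lesion that the laser catheter cannot reach or cross stays in the analysis as a Device Success failure.

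The cost is one amendment with the approvals that 16.9 requires, an updated eligibility checklist and possibly slightly slower recruitment.

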13.3 INCLUSION CRITERIA

Subjects will be enrolled in the study if ALL of the following conditions are met:

1. Patient 18 years to 75 years, both inclusive
2. Have at least one severely stenotic lesion (greater than or equal to 80% diameter stenosis as assessed by visual estimation)
3. Haemodynamically stable patients coming to the site for cardiac catheterization and angiography for various indications and who fulfill all the following criteria:

Spectranetics Corporation

Study Protocol Number: ELCA-1016

Version 1.0

Dated: 12 Oct 2016

- Have no clinically significant cardiac arrhythmias, based on ECG results
 - Have no evidence of valvular pathology, based on echocardiogram results
 - Have $\geq 30\%$ left ventricular ejection fraction (LVEF), based on echocardiogram results.
4. Angiographic evidence of calcification or a chronic total occlusion
 5. Vessel reference diameter greater than or equal to 2.0 mm
 6. Patient is willing and able to comply with study requirements
 7. Women of child bearing potential , willing to use at least two methods of contraception

13.4 EXCLUSION CRITERIA

Subjects will not be enrolled in the study if ANY of the following conditions are present in the subject:

1. Evidence of acute coronary syndrome within 3 months prior to index procedure
2. Evidence of acute ischemic events
3. Cardiogenic and non-cardiogenic shock
4. Active bleeding or coagulopathy
5. Previous coronary angioplasty within 6 months of the index procedure
6. Patients participating in trial for another investigational device/medicine within 1 month prior to enrolment in this study
7. Acute or Chronic renal failure, Impaired renal function (serum creatinine > 2.5 mg/dl or 221 $\mu\text{mol/l}$) determined within 72 hours prior to index procedure.
8. Known allergies to the following: Aspirin, Clopidogrel or Ticlopidine, Heparin, Sirolimus or its derivatives, contrast agent (that cannot be adequately pre-medicated), or any metal
9. Planned surgery within 6 months of enrollment in this study
10. Life expectancy less than 6 months
11. Patients known to be suffering from substance abuse (alcohol or drug)
12. Patients with any other significant co-morbid illness which in the opinion of the investigator is not conducive of inclusion in the study.
13. Known or suspected Pregnancy
14. Patients not willing to provide written informed consent
15. In the investigators opinion subjects will not be able to comply with the follow-up requirements.

13.5 SCHEDULE AND PROCEDURES

Prescreening Evaluation, Informed Consent & Enrollment

The subjects being considered for percutaneous coronary interventions should be pre-screened via a general review of inclusion/exclusion criteria without any study related assessment.

After the subject signed the IRB/IEC approved informed consent, study specific screening assessments can be started and the subject is provisionally enrolled.

Each potential subject who meets the inclusion criteria and has none of the exclusion criteria will be explained about the study and study device, informed about the objective, potential risks-benefits and alternatives of the study and then invited to voluntarily participate in the study. Subjects will be informed about the one month (30±7 days) follow up visit to assess the safety and efficacy endpoints. Investigator will answer each questions asked by subject and/or subject's representative during the informed consent process.

Investigator will give ample time to subject and/or subject's representative to read and understand the informed consent form. If a subject and/or subject's representative voluntarily agrees to participate in the study, subject and/or subject's representative will sign and date the written subject informed consent form prior to any study procedure. Each subject is free to withdraw from the study at any time during the study period.

Informed consent should be obtained in accordance with the applicable Indian regulations - Schedule Y and all applicable amendments (Drugs and Cosmetics Rules, 1945), GCP for Clinical Research in India (2001), ICMR guidelines for Biomedical Research on Human Subjects (2006), and current versions of Declaration of Helsinki, ICH-GCP and ISO 14155. If a subject might be eligible for the study, the investigator or delegated staff should approach the subject to obtain the written informed consent. During the consent process the background of the proposed study, the benefits and risks of study participation should be explained in detail to the subject.

It has to be emphasized that a subject's participation in the trial is voluntary and that the subject may refuse to participate or withdraw from the trial, at any time, without penalty or loss of benefits to which the subject is otherwise entitled. The subject must be given ample time to read the subject information and to address questions before signing the consent form. The Patient Information Sheet and a copy of the EC approved signed consent form (by investigator and subject) will be handed over to the subject.

13.6 SCREENING/BASELINE EXAMINATIONS

After signature of the informed consent, the subjects will undergo a baseline examination in order to assess their eligibility through the following tests and examinations

- Physical examination and relevant medical history, including angina status or myocardial ischemia assessment as per Canadian Cardiovascular Society (CCS) Classification, medication list, vital signs and subjects demographic information;
- Baseline cardiac biomarkers (CK, CK-MB and Trop I) must be obtained 24 hours prior to the index procedure;
- Routine clinical laboratory testing including Complete Blood Count (CBC) and platelet count and blood chemistry include serum sodium, potassium, urea, creatinine, and random blood sugar (RBS) must be obtained, 72 hours prior to the index procedure;
- For women of child bearing potential, urine pregnancy test must be performed 72 hours prior to the index procedure and it must be negative;
- 12-lead electrocardiogram must be obtained 24 hours prior to the index procedure.
- Documented LVEF through the Echocardiography or LV angiography to assess Left Ventricular function 72 hours prior to the index procedure.
- Review of inclusion and exclusion criteria

13.7 ANTI PLATELET MEDICATIONS

Before the procedure and in the follow-up period, the subjects will be treated with anti-platelet medications, or vasodilators, according to the standard institutional practice. Pre medication & Post medication will be recorded in Study Medication Form in eCRF.

13.8 TREATMENT PROCEDURE

The entire procedure will be carried out as per the site routine practice and the device will be used as per the 'Instruction for Use', available with Excimer Laser Coronary Atherectomy (ELCA[®]) Products.

All study investigators and site personnel involved in the clinical trial have to sign the Site Signature and Responsibility log (Delegation Log) and provide signed and dated curriculum vitae (CV).

Treating physicians/ study investigators will be trained by the study Sponsor on the study protocol and procedures prior to clinical investigation procedure.

Subject preparation and percutaneous access should be performed according to the standard hospital practice. Both femoral and radial accesses are accepted. The procedure begins once percutaneous access has been made.

13.9 POST PROCEDURE ASSESSMENT (UNTIL DISCHARGE)

The index procedure will be considered as complete, when the guiding catheter has been removed from the subject and the subject has left the cardiac catheterization laboratory. If a guiding catheter is reinserted thereafter, it will be considered as a re-intervention. Relevant CRF will be completed for such re-intervention. Following post procedure parameters will be assessed after the Coronary Atherectomy:

1. Vital Signs

Subject's vitals will be assessed immediately post PCI as per the Investigator's discretion.

2. Laboratory Evaluation

Cardiac biomarkers (CK, CK-MB and Trop I) will be performed 06-24 hours / or at discharge of post-procedure whichever is earlier. If the cardiac biomarkers (CK-MB or Trop I) are 3 times above the upper limit of normal or in case of Sub Acute Thrombosis (SAT), CK, CK-MB & Trop I must be evaluated every 8 hours until it returns to normal or until hospital discharge.

3. Electrocardiogram

12-lead electrocardiogram will be obtained 24 hours post procedure. Electrocardiograms should also be obtained for any episodes suspicious for coronary ischemia or SAT during the baseline hospitalization.

13.10 SUBJECT FOLLOW-UP

After study procedure, all enrolled subjects will be followed through hospital discharge and will undergo on-site follow-up evaluations at one month (30±7 days). The investigator may examine the subject at any time post-device placement if there is any concern about the device or subject. In addition, the investigator will inform the subject and/or subject's representative that they should report any discomfort immediately.

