	Clinic follow up visit	30 ± 7 days
	Protocol guided follow-up of patient is vital; Investigators and Site study management team should ensure minimizing follow up lapses and to avoid subjects becoming Lost-To-Follow-Up.	
Study Procedure/ Methodology	Each subject will be followed from enrollment through 30 days ± 7 days for the effectiveness and safety endpoints.	

Spectranetics Corporation

Study Protocol Number: ELCA-1016

Version 1.0

Dated: 12 Oct 2016

	
Upon enrollment after obtaining a written informed consent, each patient will be assigned a unique identification number. Only patients eligible to undergo cardiac catheterizations as per routine practice will be considered for the study. Premedication of patients will be as per the investigator's routine practice. All patient data will be recorded on patient data forms.
 
Screening: This will be performed prior to the cardiac catheterization procedure. Only patients who have consented and fulfill the selection criteria will be enrolled. Additionally, ECG and Echocardiogram will be done using hospital equipment to ensure fulfillment of inclusion/exclusion criteria.
 
Procedure: The entire procedure will be carried out as per the site routine practice and the device will be used as per the IFU.
 
Clinic follow up visit (30 ± 7 days): The subject will return to the clinic at 1 month to evaluate angina status as per the CCS classification, AE assessments, concomitant medications and any coronary intervention that has occurred since the previous contact. An electrocardiogram (ECG) will be repeated during the clinic visit.

Key Inclusion Criteria
	
The subjects have to meet the following inclusion criteria:
 
 • Patient 18 years to 75 years, both inclusive • Have at least one severe stenotic lesion (greater than or equal to 80% diameter stenosis as assessed by visual estimation) • Hemodynamically stable patients coming to the site for cardiac catheterization and angiography who fulfill all the following criteria: 
 ▪ Have no clinically significant cardiac arrhythmias, based on ECG results ▪ Have no evidence of valvular pathology, based on echocardiogram results ▪ Have $\geq 30\%$ left ventricular ejection fraction

Spectranetics Corporation

Study Protocol Number: ELCA-1016

Version 1.0

Dated: 12 Oct 2016

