12.2 STUDY POPULATION

Up to 30 patients will be enrolled at up to 05 Indian study sites. Patients will be followed from enrollment through 30 days \pm 7 days for the effectiveness and safety endpoints at the study centre.

The center's compliance to the clinical investigation plan will be assessed on an ongoing basis. In case of serious non-compliance, the sponsor may decide to stop patient enrollment in a center based on its assessment

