12.3 STUDY DURATION

Duration of this clinical study is up to 12 months which includes trial set-up, enrollment period, study procedures, follow-up visits, data analysis and release of the clinical study report.

Study will start upon the receipt of the central Indian regulatory authority's approval as well as Ethics Committee approval at respective sites. Up to 30 eligible subjects will be enrolled in the study. All subjects will be followed clinically until one month (30 \pm 7 days), post-procedure.

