12.5 STUDY ENDPOINTS

Efficacy Endpoint:

- Device Success: Successful crossing of the ELCA Catheter across the entire length of the stenotic lesion
- Procedural Success: Target lesions with less than 50% residual stenosis after laser and adjunctive therapy

Safety Endpoint:

- Freedom from major adverse cardiac events (MACE) through hospital discharge and at one month
MACE is defined as Death, Non-Q-wave and Q-wave myocardial infarction (MI), Target Lesion Revascularization, Cardiac Tamponade and Life-threatening arrhythmias
- TIMI Flow
- Lesion Morphology
- Device-related complications
- Procedure-related complications

In order to fully characterize the procedure, information of all treated lesions will be collected irrespective of whether the lesion has been treated with ELCA[®] product.

Electronic Case Report Forms will be utilized to collect relevant information.

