13.12 UNSCHEDULED CLINIC VISIT

If the subject is seen by the investigator between scheduled follow-up visits (not a study required visit), unscheduled follow-up CRF must be completed. The subject will still be required to come for the next scheduled follow-up visit if the unscheduled visit is out of the compliance follow-up window. If the subject has complications attributable to the study procedure and seeks medical advice from the Investigator between scheduled follow-up visits, an Event Reporting CRF must be completed in addition to a Follow-up CRF.

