13.16 STUDY EXIT

Every subject should be encouraged to remain in the study until they have completed the CIP required follow-up period of one month (30±7 days). If a subject prematurely discontinues the study, the reason for discontinuation should be documented in Case Report Form (CRF). Possible reasons for premature discontinuation may include, but are not limited to the following:

- For any reason determined by judgment of the investigator that the subject should no longer participate in this trial.
- Subject non-compliance with the CIP
- Subject lost to follow-up.
- Voluntary decision by the subject.
- Death

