13.17 STUDY COMPLETION

Subject who completes all protocol-required study procedures.

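### The one-month visit that closes MACE collection may fall anywhere from day 23 to day 37, so compliant subjects are observed for unequal periods and some for less than 30 days

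*Protocol*

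**What the plan says.** The first-listed safety endpoint in Protocol 12.5 is "Freedom from major adverse cardiac events (MACE) through hospital discharge and at one month". The schedule in Section 8 has one planned contact after discharge. Section 13.10 says subjects "will undergo on-site follow-up evaluations at one month (30±7 days"), and 13.11 repeats the window. Section 13.16 describes a subject who has "completed the CIP required follow-up period of one month (30±7 days"), so the required period can be met from day 23.

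Three further rules determine when event collection stops:

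- 13.17 defines study completion as "Subject who completes all protocol-required study procedures". The one-month visit is the last scheduled one.
- 14.2 limits adverse event reporting to the time before a subject's study exit or study completion.
- 16.8 makes a procedure a timing deviation only when it falls outside the allowed window.

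Section 13.12 says that a subject with an unscheduled visit is still "required to come for the next scheduled follow-up visit if the unscheduled visit is out of the compliance follow-up window". By implication, though not in so many words, an unscheduled visit inside the window can replace the scheduled one.

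The start of follow-up is worded in two ways. The synopsis says "Each subject will be followed from enrollment through 30 days ± 7 days for the effectiveness and safety endpoints", and 12.2 likewise says "Patients will be followed from enrollment through 30 days" (with the same ±7 days). Section 12.3 says "All subjects will be followed clinically until one month" and specifies that this is post-procedure.

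**The concern.** A ±7-day window is ordinary for a measurement taken at a visit, such as angina class. Here the same visit has two other functions. It is the sole scheduled post-discharge ascertainment of an event endpoint, and attending it ends event reporting for the subject. A claim of freedom from events needs observation up to its time point, and the protocol does not secure that for subjects who attend early and on protocol.

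The study has a single arm, so no control group shares the same shortfall. The one-month MACE-free proportion will stand alone and may be set beside 30-day rates from elsewhere. This point concerns subjects who complete within the window, not those who withdraw or are lost.

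**Working it through.** **Inputs from the Protocol.** Visit window 30 ± 7 days (13.10, 13.11). Sample size 25 + 5 = 30 (Section 15), which reproduces. Completion and end-of-reporting rules from 13.17 and 14.2. The only MACE rate in the document is 8.6%, from a multicentre acute-MI study described in Section 9. It serves only as an illustration, because 13.4 excludes acute coronary syndrome within 3 months and no time point is given for the figure.

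**Observation time.**

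- Earliest compliant visit: 30 − 7 = day 23. Latest: 30 + 7 = day 37.
- Spread among compliant subjects: 37 − 23 = 14 days, a ratio of 37/23 = 1.61.
- Shortest coverage of a 30-day period: 23/30 = 76.7%. Uncovered: 7/30 = 23.3% (days 24 to 30).

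**Does anything else cover days 24 to 30?** No telephone contact, day-30 status check or vital-status query is specified for a subject already seen. Section 14 has adverse events followed until study end, but this does not require new events to be collected from a subject who has completed, and 14.2 is the specific rule on when reporting stops.

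**Size, worst case.** Suppose all 30 subjects attend on day 23. Let p be the true 30-day MACE rate (assumed), with cumulative hazard H(t) = H30 × (t/30)^k and H30 = −ln(1 − p). Here k = 1 is a constant hazard, and smaller k loads events earlier. Then

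expected missed events = 30 × [p − (1 − exp(−H30 × (23/30)^k))].

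| Assumed p | k = 1 | k = 0.5 | k = 0.2 |
|---|---|---|---|
| 3% | 0.21 | 0.11 | 0.05 |
| 5% | 0.34 | 0.18 | 0.08 |
| 8.6% | 0.58 | 0.31 | 0.13 |
| 10% | 0.67 | 0.36 | 0.15 |
| 15% | 0.99 | 0.52 | 0.22 |

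Worked line for p = 8.6%, k = 1: H30 = 0.0899; 0.0899 × 0.767 = 0.0689; 1 − exp(−0.0689) = 6.7%; 30 × (0.086 − 0.0666) = 0.58. For k = 0.5 and 0.2 the recorded rates are 7.6% and 8.2%.

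**The opposite extreme.** If all 30 attended on day 37 with p = 8.6%, the recorded rates would be 10.5%, 9.5% and 8.95% for k = 1, 0.5 and 0.2. That adds about 0.57, 0.27 and 0.11 events after day 30. The two extremes are of similar size and opposite sign.

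**Scale of one event.** 1/30 = 3.3 percentage points. This is the step size of the estimate, not an estimate of bias.

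**The case against.** The best defence is that the protocol is consistent with itself. It says one month, writes that repeatedly as 30 ± 7 days, and names the same interval as the follow-up for the safety endpoints. There is no 30-day MACE endpoint and no rule on how a day-23 subject is counted. Counting, censoring or a time-to-event analysis can be left to the analysis plan, which is not shown. This stands as far as it goes: the document does not contradict itself on the window, and a reader should not say that it credits day-23 subjects with 30-day freedom from MACE. It does not answer the collection problem. An analysis plan can censor early attenders, but it cannot recover events that the protocol stopped collecting.

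The subject is also told to report any discomfort immediately (13.10). That is passive reporting and does not extend the period in 14.2.

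Three stronger readings are tempting, and the document does not support them:

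- *The window always favours the device.* This is true of early visits only. Late visits can add events from days 31 to 37, and attendance is unknown.
- *Counted from a day −10 enrollment, the earliest visit is day 13, leaving 17 of 30 days (57%) uncovered.* The synopsis sets the procedure at day 0 with the clinic visit following at 30 ± 7 days, 12.3 says post-procedure, and 13.10 places follow-up after the study procedure. Section 13.5 makes a consented subject only provisionally enrolled. The enrollment wording more naturally says when observation starts. It is loose, not a second clock.
- *Sites will differ systematically.* All sites share one window, and nothing in the document indicates such differences.

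**Conclusion.** The point holds in limited form and is of minor to moderate severity. Compliant subjects may be observed for anything from 23 to 37 days for the same endpoint, and those seen on days 23 to 29 have up to 7 of 30 days without event collection. This follows directly from 13.10, 13.17 and 14.2.

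The likely numerical effect is small: under one expected event in 30 even in the worst case, for assumed 30-day rates of 3% to 15% and the hazard shapes above. It is smaller still if visits spread across the window or, as is plausible for procedural complications, events cluster early. The net direction cannot be stated in advance. Section 15 gives no performance goal or test that the effect could overturn, and the sample size is unaffected. The case for acting is that the loss cannot be repaired at analysis and costs little to prevent.

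**What to change.** 1. In the synopsis, 12.2, 12.3, 12.5 and 13.11, state that day 0 is the index procedure and that one-month MACE means events from day 0 through day 30. Replace the enrollment wording in the synopsis and 12.2 so that it agrees with 12.3.
2. Either set the visit window to days 30 to 37, or keep ±7 days and require a documented MACE status call on or after day 30 for anyone seen on days 23 to 29. Apply the same rule to an unscheduled visit that stands in for the scheduled one under 13.12.
3. In 13.17 and 14.2, provide that completion and the end of adverse event reporting do not come before that visit or call.
4. Report events after day 30 separately.

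The cost is a protocol wording change plus either a narrower visit window or one short call by existing site staff for early attenders. The reported MACE-free rate may be slightly less favourable. Treatment and sample size do not change.
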